Costs: Both direct and indirect costs associated with PN will be included. Costs associated with the initial newborn hearing screen will be excluded from analyses since these costs are incurred for all infants regardless of outcomes. Direct costs include the cost of: PN establishment (PN recruitment and training costs), program implementation (office space, PN time, PN travel and tools, PN materials, PN supervision, staff turnover), parent time and travel (travel to seek diagnostic or PN services, time spent receiving diagnostic services), treatment costs (costs of a rescreen or diagnostic audiology appointment), nonmedical costs (potential cost savings due to earlier identification), and non-adherence costs for the clinics (no-show appointments). Research activity costs (e.g., data collection, human subject protection training of PNs) are not included. Indirect costs include opportunity costs of time (e.g. loss of productivity/wages) for the parent(s). Cost data will be collected and monitored annually throughout the study period, for both the intervention and standard of care conditions. Unit program costs will be documented as Aims 1 and 2 are implemented and sustained over the study period. Unit costs of PN and parent participant travel will be estimated using the distance between patient and clinic address/zip code multiplied by the standard GSA standard mileage rate and adding any lodging expenses (if applicable). Unit costs of PN time and PN supervision will be estimated using logs maintained by the PNs and supervisors, applying the hourly PN pay rate (or related rate for supervisor). Parent participant time will be estimated using the average wage rate for Kentucky (estimated using average wage data from the Bureau of Labor Statistics (BLS)). Unit treatment costs will be estimated using administrative charge data from the OCSHCN, aggregated at the clinic level. Unit cost savings associated with early identification will be estimated using data from the literature. Unit costs of non-adherence will be based on costs of PN time not used but spent (which may vary if services are centralized versus local) and staff costs associated with rescheduling as documented in staff logs. Loss of productivity will be estimated using an estimate of time away from work (calculated using driving distance) and lost wages for one parent, using BLS average wage statistics. Where cost related data are tied directly to PN reporting/logs, data will be reviewed and checked monthly to ensure consistency and check validity.

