Remote clinics will only be performing standard care and will not be altering any process for this study EXCEPT to notify the study personnel of a failed or irregular newborn hearing screen so that a navigator may be assigned.

The study does not require any special space. A patient navigator is not expected to be a care provider in this study, but rather an advocate for patients to identify concerns or questions, and to help patients navigate through the healthcare system. A phone in a private area of the Audiology clinic will be utilized with an encrypted, password protected computer for data collection and entry. The patient navigator has specialized skill to work with families who have a child with hearing loss and follows Good Clinical Practice when speaking with families. Research staff have experience and training in clinical research and utilize the principles of Good Clinical Practice when screening and enrolling. All have completed appropriate and documented Human Subjects Protection training.

Cyracom is an American Translators Association language interpretation and translation telephone service widely used in medical practice to assist in reaching people who do not speak English. University of Kentucky Healthcare system utilizes this phone approach for medical interpretation and translation and can be used for any language either over the phone or in direct contact. Cyracom also provides translated documentation that is certified and provide attestation to the accuracy of services.

We will also be using REDCap to collect and store data for this study. REDCap is a secure web platform for building and managing online databases and surveys. Only members of the study team will be granted access to the REDCap database.

[name], is being added from the University of Louisville as a co-investigator and will be relied upon for her expertise and advice.

[name] is a college student from Campbellsville University who will be helping with the study in data collection, recruitment, and other study processes for the summer of 2021. A reliance agreement was executed & signed.

The research will occur within 10 OCSHCN clinic offices across the state. This is a expansion of research conducted within this location approved under IRB protocol.

Potential Risks & Benefits

Risks

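### The Aim 3 costing rules would likely count unused navigator time twice and leave room for parent time to overlap, so PN's incremental cost may be overstated

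*Combined protocol and SAP*

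**What the plan says.** The operative text is the Costs paragraph under Research Procedures, Specific Aim 3. The Study Design section repeats the categories without the pricing rules.

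- **Navigator time as a program cost:** "Unit costs of PN time and PN supervision will be estimated using logs maintained by the PNs and supervisors", multiplied by the hourly pay rate.
- **Navigator time within the no-show cost:** "Unit costs of non-adherence will be based on costs of PN time not used but spent", together with clinic staff costs of rescheduling.
- **Parent time as a direct cost:** the category is "parent time and travel (travel to seek diagnostic or PN services, time spent receiving diagnostic services". On price, "Parent participant time will be estimated using the average wage rate for Kentucky", taken from Bureau of Labor Statistics (BLS) data.
- **Parent travel:** "Unit costs of PN and parent participant travel will be estimated using the distance between patient and clinic address/zip code", multiplied by a mileage rate, plus any lodging. This line prices distance, not hours.
- **Parent time as an indirect cost:** "Loss of productivity will be estimated using an estimate of time away from work (calculated using driving distance) and lost wages for one parent", also at BLS average wages.

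Two other sections bear on this. Research Procedures, Specific Aim 2 has navigators keep logs of their time, travel, attendance, family contacts and other delivery activity. Records, Privacy, and Confidentiality describes them as hourly university employees, paid for training and for delivering navigation. No section says that the two navigator lines, or the two parent lines, cover different hours.

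**The concern.** The numerator of the cost-effectiveness ratio is the difference in cost between PN and standard of care. Navigator hours arise only under PN, so any hour counted twice goes in full into that difference. Parent hours arise in both conditions, but a double count does not cancel: PN is meant to raise attendance, so more of the duplicated appointment hours would fall on PN. Both errors would make PN look more expensive per additional infant diagnosed on time. Even if neither occurs, two analysts working from this text could build different numerators from the same data.

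**Working it through.** The documents give no wage, pay rate, hours per visit, unit cost, incremental cost or ratio, so there is no stated figure to reproduce. The check traces the rules first, then gives an illustration on assumed prices.

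**Navigator lines.** Time that was paid for but went unused is still paid time. With hourly staff and general logs, it would normally sit in the logged program hours. The non-adherence rule prices it again, and nothing subtracts it. The over-count is zero only if the logs leave that time out.

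**Parent lines.** The direct line names hours receiving diagnostic services. The indirect line is an absence from work whose length is derived from driving distance. Read as appointment hours plus driving hours, nothing is counted twice. Read as the whole absence, the indirect line includes the appointment again. The text does not choose.

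**Illustration: inputs**
- Non-adherence is 7% under PN and 38% under standard of care, from the earlier academic-setting trial described under Background. Attendance is then 0.93 and 0.62, a difference of 0.31.
- Assumed, not in the documents: one attended visit per adherent referral and one no-show per non-adherent referral; parent wage $15 to $35 per hour; appointment 1 to 2 hours; navigator pay $15 to $25 per hour; 0.5 to 2 navigator hours lost per no-show; staff rescheduling cost $5 to $20.

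**Navigator over-count per PN referral** = PN non-adherence × pay × hours lost
- Low: 0.07 × 15 × 0.5 = $0.53. High: 0.07 × 25 × 2 = $3.50.
- If PN had no effect and non-adherence stayed at 38%: 0.38 × 7.50 = $2.85 to 0.38 × 50 = $19.00.
- If the logs exclude this time: $0.

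**Effect on the incremental non-adherence cost**
- Staff rescheduling only: (0.07 − 0.38) × 5 = −$1.55, or (0.07 − 0.38) × 20 = −$6.20.
- With navigator time added as written ($0.53 to $3.50): −$1.02 to +$1.95 at $5 rescheduling; −$5.67 to −$2.70 at $20. The shift is an error only where the same hours are also in the program line.

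**Parent over-count in the increment, per referral** = 0.31 × wage × appointment hours
- Low: 0.31 × 15 × 1 = $4.65. High: 0.31 × 35 × 2 = $21.70.
- Under the appointment-plus-driving split: $0.

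**Per additional on-time diagnosis** (divide by 0.31): navigator $0.525/0.31 = $1.69 to $3.50/0.31 = $11.29; parent $4.65/0.31 = $15 to $21.70/0.31 = $70; zero in both cases on the non-overlapping readings.

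**The case against.** The strongest reply is that the plan can be read without overlap. The direct parent hours are hours receiving services, travel is priced by mileage, and lost productivity is driven by driving distance. That points to appointment hours on one line and driving hours on the other. This stands: parent overlap is possible, not established. For navigators, the logs are tied to checklists for each phone call, so they may miss paid time that went unused. That also stands as a possibility, although the same logs are said to cover other delivery activity and expenses.

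The Objectives section sets a third-party-payer perspective for Aim 3, under which parent time and lost wages would not be payer costs. If that perspective were followed, the parent half would be moot. The costing text nevertheless includes parent time, and that conflict is a separate matter. The grant application to which the plan refers is not among the documents and may define the lines further.

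A reader might infer more than the documents support:
- **That a navigator component confined to PN is biased in itself.** It is not. Unused navigator time is a real cost of PN and correctly zero under standard of care. The fault lies only in entering it twice.
- **That both parent lines cover the whole trip, doubling parent time.** The direct line names time receiving services, so it gives no basis for adding travel hours there.
- **That rescheduling logs contradict the Resources section**, where clinics "will not be altering any process for this study EXCEPT to notify the study personnel". That passage concerns clinics' care processes, and existing staff records could serve as the logs.
- **That the higher non-adherence rate under standard of care gives its number of no-shows.** The plan records no-show appointments separately from late diagnosis, and a late-diagnosed infant may have none or several.

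**Conclusion.** The point holds as a likely double count of navigator time and a possible overlap of parent time. Any over-count of navigator hours raises PN's incremental cost; any overlap of parent hours does so if PN raises attendance. It would go too far to say that the incremental cost is misstated: the size cannot be determined from the documents and the lower bound is zero for both. The illustrative ranges, up to $3.50 per PN referral for navigators at 7% non-adherence and up to $21.70 per referral for parents, rest entirely on assumed prices and hours and on the earlier trial's rates. They show direction and rough scale only. The change is worth making because it settles the Aim 3 numerator at almost no cost.

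**What to change.** Revise the Costs paragraph under Research Procedures, Specific Aim 3, before the cost data are analysed:

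1. Cost navigator hours once, from the logs at the pay rate. Remove unused navigator time from the unit cost of non-adherence, or subtract it from program time. Removal needs no new data once it is confirmed that the logs capture unused paid time; subtraction needs the logs to identify those hours.
2. State that direct parent time is appointment hours and that lost productivity is travel hours only, so that each parent hour is counted once.
3. Price a no-show by the clinic staff rescheduling cost, on the same basis in both conditions. First confirm that no-show counts exist for standard of care: the Parent-Infant Measures text promises them for enrolled infants, who are recruited only under PN, and for non-participants names only outcomes on follow-up diagnostic testing. The plan has no price for an unused clinic slot, so the rule should not depend on one.

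The cost is mainly rewording, plus the check on no-show data, with no new participants. The small downside is that unused navigator time is no longer shown as a separate non-adherence cost.

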SUBJECT DEMOGRAPHICS**0 unresolved comment(s)**Age level of human subjects: (i.e., 6 mths.; 2yrs., etc.) to **Study Population:**

Describe the characteristics of the subject population, including age range, gender, ethnic background and health status. Identify the criteria for inclusion and exclusion.

Provide the following information:

- A description of the subject selection criteria and rationale for selection in terms of the scientific objectives and proposed study design;
- A compelling rationale for proposed exclusion of any sex/gender or racial/ethnic group;
- Justification for the inclusion of vulnerable groups such as children, prisoners, adults with impaired consent capacity, or others who may be vulnerable to coercion or undue influence.

Please consider these resources:

[NIH Diversity Policy](#)

[FDA Diversity Guidance](#) 

Specific Aim 1:

Based on our preliminary research, we anticipate enrolling 66% of all dyads, for a total of 1120 dyads. Once a clinic crosses from standard of care to PN in the stepped-wedge design, recruitment of all eligible parent-infant dyads in that clinic will begin. Prior to postnatal hospital discharge, parents whose infants fail their newborn hearing screening test are referred to university-based, private, or OCSHCN hearing centers for follow-up testing. The referral and contact information for these parents is collected and maintained by the state EHDI program. Within one week of postnatal hospital discharge, research personnel will contact by phone each parent referred to a OCSHCN clinic in the PN condition to describe the study, screen the parent-infant dyad for eligibility, and invite eligible dyads to enroll in the study. Informed consent will be obtained including permission to access infant hearing data from EHDI.

Inclusion criteria for parent-infant dyads:

1. Infant failed a hearing screening in one or both ears before postnatal hospital discharge
2. Infant was referred for follow-up diagnostic testing at one of the 10 participating CCSHCN clinics.
3. Parent able to speak English or another language using Cyracom, telephone interpreting service.

Exclusion criteria:

1. Children and parents live outside Kentucky or who will be moving out of Kentucky within the first three months of life.

Inclusion Criteria for Patient Navigators:

1. Age 21 years or older
2. Able to speak and read English
3. Willing to complete PN training and deliver PN.

Inclusion Criteria for Patient Navigators:

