Aim 1 is involving the recruitment of 1120 parent-infant dyads over the course of 4 years referred for hearing testing to Office for Children with Special Health Care Needs (OCSHCN) clinics all across the state of Kentucky. The research will occur within 10 OCSHCN clinic offices across the state. This is a expansion of research conducted within this location approved under IRB protocol. These patients are referred to those clinics from birthing hospitals at the time of birth because the child fails a newborn hearing test in the newborn nursery. This is one while the child is in the hospital but usually no more than 3-4 weeks after the child is born. Once the dyad is referred to that OCSHCN clinic, the clinic schedules them for their office visit in that clinic. The OCSHCN staff (not any of our research personnel) ask the parent about being contacted by the research personnel and may insert a small flyer on the study that would accompany the appointment reminder if parent would like further information. If they agree to being contacted then the clinic staff send the name and contact number of the dyad to our research staff to contact about participation in the study. We do not cold call anyone and we do not go through any records to identify subjects. The potential participants are given to us by our partners at the OCSHCN. We then contact them by phone and go through the verbal consent over the phone. We do ask parents for additional contact methods, such as email or other contact, such as text messaging and make contact up to 5 times to participate if parent does not answer or requests return call initially. After one phone conversation, we may try to text the parent with general information to gauge further interest in participation. The text message would recall the research personnel he or she spoke to, a brief summary of the study and to contact research personnel if interested. The text would be sent only after initial contact to verify the parent phone number is correct. We will attach this form to OCSHCN referral form. We will not be going through any medical records at that OCSHCN clinic where there are going to be seen before, during, or after participation in the study. The participants provides any important medical information on the study questionnaire once informed consent is obtained. We do not have any physical contact with the proposed participants as they are likely many miles away and we do not have research personnel at the clinic. Doing the consent over the phone is the

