b) Patient navigators will be identified in collaboration with our Community Advisory board, stakeholders from the OCSHCN, and leadership for the Kentucky Chapter of Hands & Voices. We will also recruit navigators from an existing pool of parents/patients who have requested to be involved in hearing healthcare research and patient advocacy maintained by Kentucky's OCSHCN. Three navigators will be needed at each of the 10 clinics (n=30). At least one bilingual (Spanish-English) navigator will attempt to be recruited for each site, but we will also utilize Cyracom, an ATA certified interpretation service to contact parents throughout the research procedures. In the case of turnover, new PNs will be identified and trained.

c) Lastly, one clinic administrator, one staff member, and one hearing healthcare provider from each of the OCSHCN clinics (n=30) will be recruited to participate in key informant interviews and to complete quantitative measures related to Aim 2.

As described above, staff at the OCSHCN will identify all infant referrals to a clinic in the intervention period and provide parent contact information to the UK research team. A CITI-trained interviewer with experience in recruiting and enrolling participants in human subjects research will describe the study, screen the parent-child dyad for eligibility, and invite eligible dyads to enroll in the study. Verbal informed consent for study participation will be obtained at that time from the parent of the eligible child on behalf of the parent and of the child. The infant will not be able to provide assent. This study will require a waiver of documentation of informed consent, as it is not feasible to obtain the written consent of all participants due to the large number and distance between OCSHCN clinics and the University of Kentucky.

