- *Research Repositories:* If the purpose of this submission is to establish a Research Repository (bank, registry) and the material you plan to collect is already available from a commercial supplier, clinical lab, or established IRB approved research repository, provide scientific justification for establishing an additional repository collecting duplicate material. Describe the repository design and operating procedures. For relevant information to include, see the [UK Research Biospecimen Bank Guidance](#) or the [UK Research Registry Guidance](#).

(See p.133 and following of attached grant submission)

For Specific Aim 1:

We will (1) use a stepped-wedge trial design to deliver patient navigation (PN) sequentially in 10 state-funded Kentucky Office for Children with Special Healthcare Needs (OCSHCN) clinics randomized to cross from usual care to PN in steps of 6-month intervals over the project period. Prior to initiation of PN at each clinic, the control condition will be the standard of care. The overall effectiveness of PN will be tested by comparing non-adherence rates during the PN condition to those during the standard of care condition. Simultaneously, we will (2) assess preliminary implementation outcomes (i.e., acceptability, adoption, recruitment/retention, and fidelity) as well as multilevel factors influencing implementation of PN in each clinic. The research will occur within 10 OCSHCN clinic offices across the state. This is a expansion of research conducted within this location approved under IRB protocol."

For Specific Aim 2:

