Aim 1 is involving the recruitment of 1120 parent-infant dyads over the course of 4 years referred for hearing testing to OCSHCN clinics all across the state of Kentucky. The research will occur within 10 OCSHCN clinic offices across the state. This is a expansion of research conducted within this location approved under IRB protocol. These patients are referred to those clinics from birthing hospitals at the time of birth because the child fails a newborn hearing test in the newborn nursery. This is one while the child is in the hospital but usually no more than 3-4 weeks after the child is born. Once the dyad is referred to that OCSHCN clinic, the clinic schedules them for their office visit in that clinic. The OCSHCN staff (not any of our research personnel) ask the parent about being contacted by the research personnel and may insert a small flyer on the study that would accompany the appointment reminder if parent would like further information. If they agree to being contacted then the OCSHCN staff send the name and contact number of the dyad to our research staff to contact about participation in the study. We do not cold call anyone and we do not go through any records to identify subjects. The potential participants are given to us by our partners at the OCSHCN. We then contact them by phone initially and go through the verbal consent over the phone. We do ask parents for additional contact methods, such as email or other contact, such a text messaging and make contact up to 5 times to participate if parent does not answer or requests return call initially. After one phone conversation, we may try to text the parent with general information to gauge further interest in participation. The text message would recall the research personnel he or she spoke to, a brief summary of the study and to contact research personnel if interested. The text would be sent only after initial contact to verify the parent phone number is correct. We will attach the contact form to initial OCSHCN referral form. We will not be going through any medical records at that OCSHCN clinic where there are going to be seen before, during, or after participation in the study. The participants provides any important medical information on the study questionnaire once informed consent is obtained. We do not have any physical contact with the proposed participants as they are likely many miles away and we do not have research personnel at the clinic. Doing the consent over the phone is the only practice way to enroll these subjects into the study in a timely manner. It is critical to do this asap because we have to involve them in the research activities within the first week or 2 after birth. If we do this by mail we will not be able to conduct this research. We will not be going through any medical records.

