Parent-Infant Dyads: As part of the same phone call to obtain parental informed consent, a trained research assistant will administer baseline measures of knowledge of hearing loss, self-efficacy for obtaining follow-up testing, and perceived barriers to follow-up testing. Alternatively, the parent can choose to complete the baseline measures via REDCap links. Following completion of baseline measures, parents will be contacted by the PN to initiate intervention delivery. Post-test measures will be administered by phone by a research assistant or via REDCap 16 weeks after birth – one month after the 3-month target deadline for diagnostic testing has passed. The research assistant administering post-test measures will not have access to data regarding parents' follow-up with diagnostic testing. Parent participants will be compensated \$20 for each set of completed measures (i.e., at baseline and at post-test assessment). These data will be shared with the CAB quarterly and recommendations on additional PN training or PN modifications will be observed. At no time during this study will prospective dyads be selected by examining medical records. Dyads will be referred by the various OCSHCN clinics, and not contacted by study personnel until that time. Additionally, no survey results, or interview information (if applicable), will be added to patient records and will only be held by research personnel for the time period required by the IRB before they are destroyed.

Parent-Infant Measures: Secondary effectiveness outcomes include parent participants' knowledge, self-efficacy, and barriers regarding obtaining follow-up diagnostic testing for their infant. We will also obtain EHDI data for all enrolled infants until their one-year birthday (or until data collection ends) to determine the time from birth to initial completed diagnostic assessment, number of no-show appointments, and number of rescheduled appointments. We will also collect data from EHDI to allow for control comparison of those infants who do not participate in the program to compare outcomes regarding follow-up diagnostic testing. From this control data, we will be conducting analyses looking at the impact of the COVID-19 pandemic on diagnostic testing and newborn hearing screening throughout the state of Kentucky. We will be comparing pre-COVID data with peri-COVID data. Additionally, we will look for racial & ethnic differences in the rates of follow up testing and screenings.

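### Enrolment contact occurs only in the PN condition and is the only described route to a navigator, yet Aim 3 has no cost item for it, so the cost per additional on-time diagnosis may be understated

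*Combined protocol and SAP*

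**What the plan says.** **When contact happens.** Subject Demographics (Study Population) states: "Once a clinic crosses from standard of care to PN in the stepped-wedge design, recruitment of all eligible parent-infant dyads in that clinic will begin". Informed Consent Process describes how the investigators receive their contacts: "staff at the OCSHCN will identify all infant referrals to a clinic in the intervention period and provide parent contact information to the UK research". Study Design says of the earlier months: "Prior to initiation of PN at each clinic, the control condition will be the standard of care". No matching contact is described for control-period parents.

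**What the contact is.** The Aim 1 recruitment text appears in Study Population, Informed Consent Process, Study Design, and Subject Recruitment Methods & Advertising. It has clinic staff "ask the parent about being contacted by the research personnel and may insert a small flyer on the study that would accompany the appointment reminder". Researchers then "make contact up to 5 times to participate if parent does not answer or requests return call initially", and may send a text after one phone conversation. Research Procedures (Specific Aim 1) adds a baseline battery on knowledge, self-efficacy and barriers, normally given in the consent call and paid at $20. Then: "Following completion of baseline measures, parents will be contacted by the PN to initiate intervention delivery".

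**What is measured.** The primary outcome is each clinic's monthly proportion of referrals that are non-adherent, compared between PN and control months. Aim 3 takes its effectiveness from the same clinic-level rates.

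**What is costed.** Study Design and Research Procedures (Specific Aim 3) list navigator recruitment and training, program implementation, parent time and travel, treatment, non-medical and non-adherence costs, and parents' lost productivity. Then: "Research activity costs (e.g., data collection, human subject protection training of PNs) are not included".

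**What clinics change.** Resources says: "Remote clinics will only be performing standard care and will not be altering any process for this study EXCEPT to notify the study personnel". The notification concerns infants who did not pass their screen.

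**The concern.** The two conditions differ by more than navigation. A parent referred in a PN month may get a staff conversation, a flyer, calls, a text and a questionnaire before the navigator calls. A parent referred in a control month gets none of these. The outcome counts referrals, not enrolled dyads, so any effect of this contact on parents who never enrol also falls on the PN side.

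Aim 3 divides a difference in cost by a difference in outcome. If the outcome difference comes from PN as delivered, including the contact that linked families to navigators, and the cost difference leaves that contact out, the ratio describes a program that was not delivered. A payer reading it would not know whether finding and reaching parents is part of the price. Separately, the plan's statement that clinic process is unchanged does not match its own recruitment text.

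**Working it through.** **1. The plan's own enrolment figure.** Informed Consent Process gives about 1,700 PN-condition referrals, 66% enrolment and 50 clinic-periods.
- 1,700 × 0.66 = 1,122, against the stated 1,120.
- 1,120 / 50 = 22.4 per clinic-period, as stated.
- Referrals not enrolled: 1,700 − 1,120 = 580, about 34%. They count in the primary outcome as worded and may have had some of the contact.

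**2. Is the contact confined to PN months?** Yes. Recruitment opens at crossover, staff pass on referrals only for clinics in the intervention period, and control is standard of care.

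**3. Does it precede the outcome?** The permission talk, calls, baseline battery and first $20 all come before navigation starts. The post-test battery and second $20 come at 16 weeks, after the 3-month window, and cannot affect the primary outcome.

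**4. Is it costed?** No listed item covers it. Navigator recruitment means hiring navigators. Navigator and supervisor logs cover their own time. The staff costs drawn from logs concern rescheduling. Enrolment calls are made by research staff. The exclusion names data collection and human-subjects training only as examples. That outreach is left out is therefore an inference from the general term and from the list's silence.

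**5. Illustrative cost of call attempts alone.** The documents give no attempt counts, minutes or wages. Assumptions: 2 to 5 attempts per referral, 5 minutes each, $20 to $30 per hour, all 1,700 referrals called.
- Low: 1,700 × 2 × 5 min = 17,000 min = 283 h; × $20 ≈ $5,700.
- High: 1,700 × 5 × 5 min = 42,500 min = 708 h; × $30 ≈ $21,300.

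This is an upper-end range. The recruitment text limits calls to parents who agreed to contact, and repeat attempts to parents who did not answer or asked for a return call. The floor of two attempts has no source. If only the 1,120 enrolled dyads were called, the same assumptions give:
- 1,120 × 2 × 5 min = 187 h; × $20 ≈ $3,700.
- 1,120 × 5 × 5 min = 467 h; × $30 = $14,000.

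Staff talks, flyers, texts and interpreter time are not in these figures. No total PN cost is given, so neither range can be set against the program's cost.

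**6. The passages that need reconciling.**

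| Topic | One place | Another place |
|---|---|---|
| Clinic process | Resources: nothing changes except notification | Recruitment text: permission talk and possible flyer |
| First contact | Study Population (opening text): researchers phone each referred parent within a week of discharge | Recruitment text: clinic staff ask first, and only agreeing parents are passed on |

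**The case against.** The other side has a good case on several points.

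- **Leaving out research costs is legitimate.** Routine adoption would need no research consent or baseline battery. If navigators made first contact, that time would be navigator time, which is already costed. This stands, and it is why consent, questionnaires and payments should stay excluded. It does not cover the trial as delivered, where other staff did the finding and linking and no cost item records it.
- **The exclusion does not name outreach.** True. The plan may intend to count it under program implementation, but does not say so.
- **This is an effectiveness trial of PN as rolled out, and asking permission is arguably part of notification.** That supports describing the intervention as delivered. It does not remove the need to cost it or to describe the clinic step consistently.

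Three stronger readings are tempting, and the documents do not support them.

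- A reader might infer that every contact prompts the hearing appointment, and so that a share of the contrast is certainly outreach. The talk asks about being contacted by researchers, the text summarises the study, the flyer and text are optional, and the $20 pays for completed measures. The flyer, script and baseline form were not available to read. No figure allows an outreach effect to be estimated, so no share can be stated.
- A reader might infer that both the effect and the cost are shown to err in PN's favour. This is plausible, because the contact precedes testing and concerns it, but it is not shown.
- A reader might add the enrolment calls to the cost: 1,120 × 20 to 40 minutes is 373 to 747 further hours on assumed durations. That call combines consent with the baseline battery, which are research activities. Adding it whole would contradict their exclusion.

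**Conclusion.** The point holds in a limited form. Contact confined to the PN condition is the only described way a parent reaches a navigator. Any effect it has is counted in the primary contrast and in Aim 3 effectiveness. Its cost has no place in the Aim 3 list and would be left out under the research-activity exclusion. The cost per additional on-time diagnosis may therefore be understated.

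The size is uncertain. The effect of outreach cannot be estimated from the documents. Call attempts alone would come to at most about $5,700 to $21,300 on the assumed attempts, minutes and wages. Whether that is material depends on a total PN cost that the plan does not give. The contradiction on clinic process holds whatever the size. This is an inexpensive improvement to the costing and wording; it does not invalidate the design.

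**What to change.** 1. **Aim 3 costs (Study Design and Research Procedures).** Keep questionnaires, participant payments, research consent and human-subjects training excluded. Add a scenario or sensitivity analysis that costs identification and linkage contact: clinic-staff talk, flyer, call attempts, texts and interpreter time. Use the Parent Phone Contact Documentation form, listed under Data Collection & Research Materials, where it records these. Its content was not available to check, so state unit-time assumptions for the rest.
2. **Objectives, Study Design and Research Procedures (Aim 1).** Word the effectiveness conclusion and the ratio as PN delivered with its outreach and enrolment contact.
3. **Consistency.** Reconcile Resources with the recruitment text on clinic process, and the opening Study Population text with the recruitment text on who makes first contact.

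The consent section records that enrolment has ended, so equivalent contact can no longer be added to control periods. The changes above need only wording and costing from existing records and stated assumptions. The price is a somewhat less favourable cost per additional on-time diagnosis in the scenario, and a slightly narrower claim.
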